### **3.5. Procedures for Identifying and Randomizing Research Participants**

Prior to initiating the study, team members will be trained on the protocol and study procedures. The background to the study, study procedures, consent processes for the online or the verbal consent, data transfer, and plans to monitor intervention integrity and data quality will be part of the training.

[figure not shown]
Following the study preparation, initial screening for eligibility, consent and additional eligibility verification for the research participants will begin. Once consented and eligibility is confirmed, participants will be randomized using a permuted-block method with random block sizes, stratified on sex, age (<40 vs.  $\geq 40$ ), and cranial radiation therapy (Y/N). Following randomization, participants will complete the remote cognitive assessment, will provide a blood sample using the Dried Blood Spot (DBS) method and wear a WHOOP wrist monitor for 7 to 11 consecutive days. Following the remote evaluation, they will receive a direct link to access the SHUTi program or online patient education (per randomization).

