### 9.1. Summary of Primary and Secondary Objectives

#### Statistical Analysis

A randomized controlled design will be employed for the proposed study. We plan to enroll a total of 352 survivors (176 of each sex), and assuming 10% drop out by the post-intervention 9-week assessment, we will have a total of 320 survivors (160 of each sex) remaining for evaluation. Balance of patient characteristics between study arms will be evaluated and if necessary, adjusted comparisons will be carried out.

The primary endpoint of the study will be the ISI measure of insomnia severity represented as described above. The difference in score from baseline to post-intervention (10 weeks) and baseline to 6 months post-intervention will be calculated and the mean of these differences compared between study arms using linear regression (adjusted for stratification factors). The primary time point of interest will be at 10 weeks, with a secondary endpoint evaluating maintenance at 6 months after intervention. Due to potential sex differences in insomnia and cognition, *a priori* we plan to carry out all analyses and report results separately by sex. Our study is not powered to detect meaningful interaction effects, but if we deem that the effects are reasonably comparable between sexes we will consider presenting combined analysis to increase precision of the estimate. Because this is a randomized trial we expect analyses to be simple and directed towards ascertaining controlled and generalizable intervention effects. The primary endpoint will be considered significant at the two-sided 0.05 level. Estimates of intervention effects (mean differences) will be presented along with associated confidence intervals and two-sided p-values.

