Because mean scores do not reflect the number of survivors who have clinically significant insomnia symptoms, secondary analyses of sleep will compare the proportion of survivors who no longer meet the clinical criteria for insomnia (ISI  $\leq 7$ ) between study arms post-intervention (10 weeks) and at 6 months (noting that 100% of eligible participants will meet the criteria at randomization), using logistic regression models. Additional measures of sleep will also be summarized and compared (sleep diary, actigraphy, fatigue, daytime sleepiness) from baseline, post-intervention, and 6 months. Using the same analytic framework as above, we will evaluate the effect of study intervention on the secondary endpoints of neurocognitive impairment: patient reported (Task Efficiency, Memory, Emotional Regulation) and directly assessed (attention, memory, and executive function) with continuous outcome measures. Additional analyses relevant to secondary objectives focus on better understanding the associations and mediating relationships between the CBTi intervention, insomnia, neurocognition, emotional distress, cardiovascular risk indices and HRQoL (see Figure 2 for theoretical framework).

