### Power and sample size

We plan to enroll a total of 352 subjects, 176 of each sex), and assuming 10% drop out by the post-intervention 9-week assessment, we will have a total of 320 subjects (160 of each sex) remaining for evaluation. The

St Jude Children's Research Hospital

IRB NUMBER: 19-0121

IRB APPROVAL DATE: 05/04/2021

stratum, with 80 survivors per study arm, 80% power and  $\alpha$  of 0.05 for the primary endpoint comparison of the ISI, we will be able to detect a minimum effect size of 0.45. We will continue to enroll participants until we have 320 evaluable at 9 weeks. Assuming a total dropout of 20% by 6 months post-intervention, there will be approximately 70 survivors within each sex per study arm available for assessment, allowing detection of a 0.48 minimum effect size. If sex specific intervention effect estimates are comparable with each other, a combined analysis among the 320 survivors evaluable at 10 weeks will be sufficient to detect an effect size of 0.31, with 80% power and two-sided  $\alpha$  of 0.05. Secondary endpoints of neurocognition will have ability to detect the same effect sizes; secondary endpoint p-values will be presented using both a nominal significance level of 0.05 and adjustments for multiple comparisons using a false discovery rate methodology.

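### The primary ISI change-score model omits baseline ISI; adding it is a nearly free gain in precision, of unknown size and possibly close to zero

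*Combined protocol and SAP*

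**What the plan says.** Section 9.1 (Statistical Analysis) makes ISI the primary endpoint, with 10 weeks as the primary time point. Changes from baseline are calculated and "the mean of these differences compared between study arms using linear regression (adjusted for stratification factors" are the only covariates named for this model. Section 3.5 identifies those factors: randomisation uses a "permuted-block method with random block sizes, stratified on sex, age" (under 40 or not) and cranial radiation (yes/no). Baseline ISI is not among them, although Section 4.3, the evaluation table in Section 5.2 and Appendix I all schedule the ISI at baseline.

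The analysis is to be run within sex: "we plan to carry out all analyses and report results separately by sex". The same model carries over to other outcomes: "Using the same analytic framework as above, we will evaluate the effect of study intervention on the secondary endpoints of neurocognitive impairment". For power, with 80 per arm within each sex, the plan states that "we will be able to detect a minimum effect size of 0.45".

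Three other statements in Section 9.1 touch on adjustment:

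- "Balance of patient characteristics between study arms will be evaluated and if necessary, adjusted comparisons will be carried out". This depends on what is observed and names no variable.
- Cumulative methotrexate, cytarabine and cranial radiation doses enter the analyses judged relevant. Baseline ISI is not listed.
- Baseline functioning is mentioned for missing-data sensitivity analyses only.

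**The concern.** Subtracting the baseline is the same as regressing the 10-week score on arm with the baseline coefficient held at 1. When the true coefficient is below 1, as regression to the mean usually makes it, the change score over-corrects and carries baseline noise into the outcome. The confidence interval is then wider than it needs to be.

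At stake is precision, not validity. In absolute width and power the loss weighs most in the sex-specific analyses, with 80 per arm at 10 weeks and about 70 at 6 months; the proportional loss is the same in a combined analysis. Section 9.1 offers pooling the sexes as a way to gain precision, but only if the sex-specific effects look comparable. Baseline adjustment pursues the same aim within each sex and needs no such judgement after seeing results.

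**Working it through.** **Inputs from the documents** (Section 9.1): two-sided 0.05; 80% power; 80 per arm within sex at 10 weeks; about 70 per arm within sex at 6 months; 160 per arm combined.

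**Inputs not in the documents, therefore assumed:** correlation rho between baseline and follow-up ISI of 0.3, 0.5 and 0.7; ratio k of follow-up SD to baseline SD of 1.0, 1.25 and 1.5. A ratio above 1 is plausible because entry can be through ISI of 8 or more, which may narrow the baseline spread. Entry is also possible on sleep-onset or wake-time criteria alone, so the degree of narrowing is unknown. SDs and correlation are taken as equal across arms.

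**Step 1: reproduce the plan's figures.** For a two-sample t test (noncentral t), the detectable standardised effects are 0.446 (80 per arm), 0.477 (70) and 0.314 (160), against 0.45, 0.48 and 0.31 stated. They agree.

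**Step 2: compare the variances.** With baseline SD s0 and follow-up SD s1:

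- change score: s0² + s1² − 2·rho·s0·s1
- baseline-adjusted: s1²·(1 − rho²)
- difference: (s0 − rho·s1)², which is never negative

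In large samples, estimating the slope therefore cannot increase the variance. The difference is zero only when the slope, rho·k, equals 1. In units of s0 the ratio of adjusted to change-score variance is k²(1 − rho²) / (1 + k² − 2·rho·k). For example, k = 1 and rho = 0.5 give 0.75 / 1.00 = 0.750; k = 1.25 and rho = 0.8 give 0.5625 / 0.5625 = 1.000.

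**Step 3: convert to power and detectable effect.** The plan does not say in which SD its effect size is expressed. Assuming SDs of change, the planned model has 80.0% power at 0.446. With baseline ISI added, power is taken at 0.446/√ratio with one degree of freedom fewer. At 80 per arm:

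| k | rho | variance ratio | interval narrower by | power | detectable effect |
|---|---|---|---|---|---|
| 1.0 | 0.3 | 0.650 | 19% | 93.5% | 0.36 |
| 1.0 | 0.5 | 0.750 | 13% | 89.9% | 0.39 |
| 1.0 | 0.7 | 0.850 | 8% | 86.0% | 0.41 |
| 1.25 | 0.3 | 0.784 | 11% | 88.5% | 0.395 |
| 1.25 | 0.5 | 0.893 | 5.5% | 84.3% | 0.421 |
| 1.25 | 0.7 | 0.981 | 1% | 80.8% | 0.441 |
| 1.5 | 0.3 | 0.871 | 7% | 85.1% | 0.416 |
| 1.5 | 0.5 | 0.964 | 2% | 81.4% | 0.438 |
| 1.5 | 0.7 | 0.998 | 0.1% | 80.1% | 0.445 |

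For the other analyses at k = 1.0 and rho 0.3, 0.5, 0.7, the detectable effect is 0.384, 0.413, 0.440 per sex at 6 months and 0.253, 0.272, 0.290 combined at 10 weeks.

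**Step 4: simulate the cost and the error rate.** There were 20,000 trials per setting, 80 per arm, with age group (assumed 50%) and cranial radiation (assumed 30%) in both models.

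- Slope exactly 1: power 79.1% planned, 78.8% with baseline ISI.
- k = 1.0, rho = 0.5: power 79.4% planned, 89.5% with baseline ISI.
- No effect: rejection 4.9% planned against 4.9% adjusted (k = 1.25, rho = 0.8), and 4.9% against 4.7% (k = 1.0, rho = 0.5).

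**The case against.** The strongest reply is that nothing here is an error. A change-score regression adjusted for the stratification factors is a legitimate pre-specified analysis, and the plan says it wants its analyses simple. That stands: this is an efficiency suggestion only.

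Nor can the benefit be sized. The largest gains need equal SDs; with a more variable follow-up they shrink to a few points or less. That also stands. The power figures further depend on reading 0.45 in SDs of change. If the effect is instead 0.446 baseline SDs, with equal SDs and 80 per arm, planned against adjusted power is 65.8% against 83.6% at rho 0.3, 80.0% against 89.9% at 0.5, and 95.1% against 97.5% at 0.7. The gain then runs from about 2 to 18 points, and the planned model is no longer held at 80%. Only the variance ratios are free of this choice, so they are the figures to rely on.

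The plan's other adjustment clauses do not fill the gap. The imbalance clause would bring baseline ISI in only after a look at the data. The treatment-exposure clause does not list it, and leaves open whether the primary model is among the relevant analyses.

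Finally, the claim that no participant is lost holds only if the covariate is the same ISI measurement that forms the change score. That condition belongs in the fix.

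**Conclusion.** The point holds as a recommended improvement, not a correction. Baseline ISI is collected and needed for the change score, yet is not a pre-specified covariate. Over the grid in the working, the variance reduction runs from 35% to 0.2%, and it is exactly zero at slope 1. In power, on the SD-of-change reading, that is a gain of zero to about 13.5 points from a base of 80%, against a worst simulated loss of about 0.3 points. The direction is certain in large samples; the size rests on assumed SDs and correlations, and a near-zero gain is plausible. The case for acting is this asymmetry, together with the value of settling the covariate before data are seen.

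**What to change.** In Section 9.1, pre-specify baseline ISI alongside the stratification factors. Within each sex the primary 10-week model would contain arm, baseline ISI, age group and cranial radiation; any combined analysis adds sex. The outcome can stay as change, because with baseline in the model the arm coefficient is the same as for the 10-week score.

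Two details should go with it:

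- **Which ISI is the baseline.** The ISI is an entry criterion, eligibility is screened in DatStat, and post-enrolment questionnaires run in RICE. Name one measurement and use it both for the change score and as the covariate.
- **Secondary endpoints.** For each continuous endpoint analysed in the same framework, use its matching baseline measured before program access. The direct cognitive baseline is taken after allocation ("Following randomization, participants will complete the remote cognitive assessment") but before access ("Following the remote evaluation, they will receive a direct link to access the SHUTi program or online patient education"), and the planned change scores already rely on it.

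As minor clarifications, label any imbalance-triggered adjustment a sensitivity analysis, and say whether the treatment-exposure covariates apply to the primary model.

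The cost is one degree of freedom per model and one or two sentences of SAP text, with no new data, no lost participants and no change in sample size.

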**Evaluation:** Eligible participants will complete a 9-week internet-based insomnia treatment program or receive sleep education, depending on group assignment. CCSS participants who have been previously identified as having neurocognitive impairment will be approached for recruitment. An approach packet consisting of an introduction letter, a single page study brochure, and informed consent documents will be mailed to potentially eligible participants. Interested participants will be able to return the consent via mail using a pre-paid envelope. Alternatively, the packet will include instructions for visiting the study webpage, where participants can sign-up and provide informed consent on-line. Those who have not responded after two weeks will receive an email alerting them to the study and providing a link to the study webpage. Starting three weeks after the initial mailing, a trained study interviewer housed within the CCSS Call Center will begin calling non-responders to provide information, answer questions, and encourage participation. Participants will have the opportunity to consent to the study verbally while speaking with the CCSS Call Center. Alternatively, survivors who wish to participate will enroll online via DatStat Connect (the current online data collection tool for the CCSS). Prospective participants will complete an online consent form. After consenting, they will complete a series of short online questionnaires to determine study eligibility. We anticipate needing to recruit 352 participants to reach the targeted enrollment of 320 at 9 weeks and 280 at 6 months. Upon enrollment, participants will be asked to complete all the study activities completely remotely. For the baseline remote evaluation, participants will complete a computerized remote cognitive assessment and will provide a blood sample using the Dried Blood Spot (DBS) method. Participants will be asked to complete online questionnaires and sleep diaries. Participants will be mailed a WHOOP wrist monitor to wear for 7 to 11 consecutive days. Two more identical remote evaluations will occur, one immediately after the intervention is completed and one 6 months after completion of the intervention.

**Study Design:** Randomized Controlled Trial

**Sample Size:** Approximately 352 research participants

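### The 6-month ISI 'maintenance' endpoint tests for an effect at 6 months, not whether the week-10 effect was kept, and its comparison leaves out about 40 people with a known week-10 score

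*Combined protocol and SAP*

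**What the plan says.** Section 9.1 (Statistical Analysis) defines two outcomes from the ISI: "The difference in score from baseline to post-intervention (10 weeks) and baseline to 6 months post-intervention will be calculated". Their means are compared between arms by linear regression adjusted for the stratification factors. Week 10 is the primary time point, "with a secondary endpoint evaluating maintenance at 6 months after intervention". All analyses are to be done and reported by sex, and a combined analysis is only something the team will consider if the sexes look alike. Mean differences are to be given with confidence intervals.

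The protocol summary (Evaluation) plans recruitment "to reach the targeted enrollment of 320 at 9 weeks and 280 at 6 months". For 6 months, Power and sample size states that "there will be approximately 70 survivors within each sex per study arm available for assessment, allowing detection of a 0.48 minimum effect size".

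Nowhere do the documents give a week-10-to-6-month contrast, a retention margin or a definition of maintenance. No mixed or repeated-measures model is named; structural equation modelling is planned for mediation only. The missing-data paragraph of Section 9.1 offers sensitivity analyses if missingness turns out to be substantial. It lists factors to consider but names no method.

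**The concern.** The label and the test answer different questions. An arm difference in change from baseline to 6 months shows whether some effect is present then. Maintenance concerns how that effect compares with the one at week 10. A significant 6-month result is compatible with losing half the effect, and a non-significant one, with fewer people, does not show that the effect was lost.

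The second issue is missing data. A 6-month change score cannot include anyone without a 6-month ISI, so about 40 people drop out of that comparison although their week-10 ISI, likely a strong predictor of the missing value, is on file. If leaving depends on week-10 ISI in a different way in each arm, the 6-month estimate is biased by a mechanism that was observed and could have been modelled.

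At stake is how the durability of the intervention is reported.

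**Working it through.** **Plan's own figures.** For a two-sample comparison with SD 1, 80% power and two-sided 0.05, the detectable effect is (1.960 + 0.842) × √(2/n).
- n = 70 per arm: 0.474 (0.477 by the t distribution), against 0.48 stated.
- n = 80: 0.443 (0.446), against 0.45 stated.
- n = 160: 0.313 (0.314), against 0.31 stated.

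The sample-size figures reproduce. People with a week-10 but no expected 6-month ISI: 320 − 280 = 40, or 12.5% of 320, about 10 per sex per arm.

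**Assumptions (the documents give no ISI SD, correlation or expected effect).** SD 4.5 at baseline and 5.5 at both later visits. Correlations 0.40 (baseline–week 10), 0.35 (baseline–6 months), 0.65 (week 10–6 months).

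- SD of change to week 10: √(4.5² + 5.5² − 2×0.40×4.5×5.5) = √30.70 = 5.54
- SD of change to 6 months: √(4.5² + 5.5² − 2×0.35×4.5×5.5) = √33.18 = 5.76
- SD of change from week 10 to 6 months: √(2×5.5²×0.35) = √21.18 = 4.60

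The SE of an arm difference is SD × √(2/n). Power is Φ(|effect|/SE − 1.96).

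| | Within sex, 70 per arm | Combined, 140 per arm |
|---|---|---|
| SE, baseline to 6 months | 0.97 | 0.69 |
| SE, week 10 to 6 months | 0.78 | 0.55 |
| Effect fades −4 to −2: 6-month test significant | Φ(2.05 − 1.96) = 54% | Φ(2.91 − 1.96) = 83% |
| Same fade: direct contrast detects the 2-point loss | Φ(2.57 − 1.96) = 73% | Φ(3.64 − 1.96) = 95% |

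**At the protocol's own detectable effect.** 0.45 × 5.54 = 2.49 points; half is 1.25. The 6-month test is then significant in Φ(1.25/0.97 − 1.96) = 25% of trials within sex and Φ(1.25/0.69 − 1.96) = 44% combined. The direct contrast detects this 1.25-point loss in 36% and 62%.

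**Range in SD units.** With equal SDs at both visits, the chance of a significant 6-month test after exact halving is as follows.

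| Week-10 effect (SD) | Within sex | Combined |
|---|---|---|
| 0.45 | 26% | 47% |
| 0.60 | 43% | 71% |
| 0.80 | 66% | 92% |
| 1.00 | 84% | 99% |

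**Bias from later loss (simulation, sexes combined).** 160 per arm at week 10, 12.5% lost afterwards with log-odds linear in week-10 ISI (slope per SD, centred within arm), true 6-month effect −3.0.

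| Dependence of loss on week-10 ISI | Completers-only change score | Joint likelihood estimate |
|---|---|---|
| Slope 0.5 to 1.2 in SHUTi, 0 to −0.5 in control | about −3.1 to −3.4 | about −3.0 |
| The same slopes swapped between arms | about −2.9 to −2.6 | about −3.0 |
| Equal slopes in both arms (0.5 to 1.2) | about −3.0 | about −3.0 |

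If instead one rule on the raw week-10 score applies to everyone, with a week-10 effect of −4, the completers-only estimate is −2.97 to −2.87, a slight understatement. The joint model's SE is about 3% smaller (for example 0.665 against 0.686).

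**The case against.** The case against has real weight.

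- **Maintenance is one descriptive word.** The outcome behind it is explicitly defined, and no hypothesis in Section 1 claims that the ISI effect is retained. Confidence intervals are promised, so −4 followed by −2 would be visible, and remission is also compared at both times. An effect of −2 at 6 months is a true effect, not a false positive. All of this stands. But two separate intervals give the reader no interval for the change between visits, and a label that promises maintenance invites a reading that the test cannot support.
- **A reader might infer that the plan would usually declare maintenance after half the effect is gone.** The documents do not support that. The 83% belongs to an optional combined analysis and an assumed −4 points (4/5.54 = 0.72 SD). For the a priori within-sex analysis it is 54%, and at the protocol's own 0.45 SD it is 25%.
- **A reader might infer that ordinary loss of non-improvers inflates the 6-month effect.** It does not follow. Inflation needs loss to depend on week-10 ISI differently by arm and in one particular direction. Equal dependence gives no material bias, and the reverse pattern shrinks the estimate. The documents do not say which pattern to expect.
- **A reader might infer that week-10 data are thrown away.** Those scores are used in the primary analysis and are absent only from the 6-month comparison. The precision at issue is small.
- **The missing-data paragraph could cover this.** It is relevant, but it is conditional and names no method, so it does not commit the plan to using week-10 ISI.
- **The direct contrast does not prove maintenance either.** This is correct. A non-significant contrast is not evidence that the effect was kept, and the fix must say so.

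**Conclusion.** The point holds as a modest, inexpensive correction to a secondary endpoint. Section 9.1 labels as maintenance an analysis that tests for an effect at 6 months, and that analysis ignores the week-10 ISI of about 40 people who are expected to leave before 6 months.

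How often a halved effect would still be significant depends on the week-10 effect, for which the documents give no expected value. It runs from about a quarter of trials (within sex, 0.45 SD) to about four in five (combined, −4 points). The possible bias is up to about 0.4 points in either direction on a true −3.0, and only when loss relates to week-10 ISI differently by arm. These sizes rest on assumed SDs, correlations and dropout slopes. The mismatch between label and test, and the 320-to-280 gap, rest on the text alone. That the two visits are analysed separately is the natural reading, since no joint model is named.

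The primary week-10 test and the stated sample-size figures are not affected.

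**What to change.** In Section 9.1, analyse week-10 and 6-month ISI in one likelihood-based repeated-measures model. Include arm by visit, the stratification factors, an unstructured covariance, and baseline ISI either as a covariate or as a visit. Fit it within sex and, if a combined result is presented, in the combined sample. Keep everyone with a baseline and at least one follow-up ISI, and take the 6-month arm difference from this model.

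Beside it, report the arm difference in change from week 10 to 6 months with its 95% confidence interval. State that maintenance is judged from that interval and that a non-significant contrast is not taken as evidence of it. Under the assumptions above and using completers only, the half-width would be about 1.96 × 0.78 = 1.5 points within sex and 1.96 × 0.55 = 1.1 combined, so the within-sex answer may be imprecise. If the team does not want this contrast, rename the endpoint the effect at 6 months.

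The cost is a change of SAP wording and one standard model, with no new data. The model relies on loss being at random given the observed scores, so the planned missing-data sensitivity analyses remain useful and should name a method.

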## 1.0 OBJECTIVES

### 1.1. Primary Objective

To examine the efficacy of an eHealth intervention for improving symptoms of insomnia among adult survivors of childhood cancer.

Hypothesis 1.1.a.: Survivors randomized to an eHealth CBTi intervention will report significantly fewer symptoms of insomnia post-intervention compared to survivors randomized to online patient education only.

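### One primary hypothesis at one 0.05 level is tested separately in each sex at an unsplit 0.05, with optional pooling after the effects are seen, and no readable rule says which result decides

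*Combined protocol and SAP*

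**What the plan says.** Hypothesis 1.1.a (Section 1.1) is one claim with no split by sex: "Survivors randomized to an eHealth CBTi intervention will report significantly fewer symptoms of insomnia post-intervention" than those given patient education. Section 9.1, Statistical Analysis, attaches one level to it: "The primary endpoint will be considered significant at the two-sided 0.05 level". The primary time point is 10 weeks.

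The same paragraph commits in advance to sex-specific analysis: "we plan to carry out all analyses and report results separately by sex". It then concedes a limit: "Our study is not powered to detect meaningful interaction effects". Pooling is nevertheless left open, in these terms: "if we deem that the effects are reasonably comparable between sexes we will consider presenting combined analysis to increase precision of the estimate".

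Power and sample size follows the same structure. With 80 per arm within a sex, 80% power and alpha 0.05, it says that "for the primary endpoint comparison of the ISI, we will be able to detect a minimum effect size of 0.45". It then sets a condition for pooling: "If sex specific intervention effect estimates are comparable with each other". Where that condition is met, the figure given is that "a combined analysis among the 320 survivors evaluable at 10 weeks will be sufficient to detect an effect size of 0.31", again with 80% power and two-sided 0.05.

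On multiplicity, the power section assigns the false discovery rate to secondary endpoints. The mediation paragraph of Section 9.1 promises p-values with and without adjustment for all effect estimates. That plausibly includes the primary mean difference, but it does not say which version decides.

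Two stretches of text are lost in the copy available: the words just before the per-sex power statement, and the start of the mediation paragraph. The statements here concern the readable text.

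**The concern.** One hypothesis with one 0.05 level is to be answered by two tests, each at 0.05. Pooling is conditional on how the two estimates look. The plan does not define comparable. It also does not say whether Hypothesis 1.1.a is supported by women alone, men alone, either, both, or only the combined result.

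Two things are at stake. First, the stated 0.05 is not guaranteed for the primary claim, because the actual level depends on a rule that has not been written. Second, if one sex is significant and the other is not, the reading of the trial would have to be settled after the results are known. The plan itself concedes that it lacks power for interaction, so the data are a weak guide to whether the sexes differ.

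**Working it through.** **Inputs.** From Power and sample size: 80 evaluable per arm within each sex at 10 weeks, 70 at 6 months, 160 per arm combined; 80% power; two-sided 0.05. Effects are in SD units. The sexes are independent and contribute equal information, as planned.

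**1. The plan's own figures.** Two-sample t-test, 80% power: 80, 70 and 160 per arm give detectable effects of 0.446, 0.477 and 0.314. The stated 0.45, 0.48 and 0.31 reproduce. Each therefore uses the full 0.05, with no split between the sexes.

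**2. Overall error with no effect in either sex, by deciding rule.** The pooled statistic is (Z_women + Z_men)/√2.

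| Rule (none is stated) | Calculation | Two-sided | False claim of benefit |
|---|---|---|---|
| Both sexes required | 0.05²; 0.025² | 0.25% | 0.06% |
| Pooled test only | single test | 5.0% | 2.5% |
| Either sex suffices | 1 − 0.95²; 1 − 0.975² | 9.75% | 4.9% |
| Either sex or pooled | integration, confirmed by simulation | 11.5% | 5.8% |

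The 0.25% applies only when neither sex benefits. If one sex truly benefits, the both-sexes rule can wrongly include the other up to 5% of the time.

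**3. How often the sexes split when the true effect is equal.** With per-sex power p at 80 per arm, exactly one sex is significant with probability 2p(1 − p).

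- 0.45 SD: p = 0.8075, so 2 × 0.8075 × 0.1925 = 31% (both 65%, neither 4%).
- 0.50 SD: p = 0.882, so 21%.
- 0.60 SD: p = 0.965, so 7%.

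**4. Whether the data can settle comparability.** The standard error of the difference between the two sex-specific effects is √2 × √(2/80) = 0.224 SD. With identical true effects, the estimates differ by more than 0.2 SD 37% of the time. With 0.45 SD in one sex and none in the other, a 0.05 interaction test detects the difference 52% of the time.

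**5. The two candidate rules.**

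- *Holm across the sexes.* Overall error is 1 − 0.975² = 4.9% (benefit 1 − 0.9875² = 2.5%). Power for one sex is P(p ≤ 0.025) + P(0.025 < p ≤ 0.05) × P(other sex p ≤ 0.025). At 0.45 SD, P(p ≤ 0.025) = 0.720 and P(p ≤ 0.05) = 0.8075. If the effect is shared: 0.720 + 0.0875 × 0.720 = 78%. If the other sex has none: 0.720 + 0.0875 × 0.025 = 72%. The detectable effects at 80% power are 0.459 and 0.490. At 0.45 in both sexes, at least one passes 92% of the time and both 64%.
- *Pooled test only.* Error is 5%. Power is 98% at 0.45 in both sexes, and 52% if only one sex responds at 0.45 (average effect 0.225).

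**The case against.** The plan does rank its analyses. Sex-specific analysis is declared in advance, the per-sex power statement is tied to the primary endpoint, and the combined analysis is optional and described as a gain in precision, which is an estimation purpose. This stands. The three results should not be treated as equal contenders, and the central gap is how two sex-specific results answer one hypothesis.

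If each sex were its own question, each test would hold 5%. That is also fair, but Section 1.1 states no such hypotheses.

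A reader might infer that the plan's error rate is 11.5%. The documents do not support that: it requires pooling to be a third route to success, which no passage says. Nor does the plan contain an interaction gate. If one is assumed, the answer turns on the fallback. For gates from 0.01 to 0.50, pooling when the gate is passed and otherwise accepting either sex gives 5.9% to 11.4%, while otherwise requiring both gives 2.6% to 5.1%.

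A reader might also infer that a split result is likely whatever the effect. The 31% belongs to 0.45 SD, the minimum detectable effect. The background in Section 2.2 cites moderate to large effects of CBTi on sleep, and at 0.6 SD the figure is 7%.

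Finally, a rule could lie in the lost text. That cannot be excluded, but the sentence that makes pooling a matter of judgement is intact.

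**Conclusion.** The concern holds as a missing decision rule for the primary hypothesis, together with a choice to pool that follows the results. The best-supported figure is 9.75% two-sided (4.9% for false claims of benefit, against 2.5%), and it applies if success in either sex counts and neither sex benefits. The other rates, from 0.25% to 11.5%, show how much depends on the unwritten rule; none is the plan's stated error rate. The error figures assume independent sexes with equal information, and the power figures use the planned evaluable numbers. It cannot be said that the trial will exceed 5%, only that the text does not ensure that it will not.

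**What to change.** In Section 9.1 and in Power and sample size, delete the two conditions that make the combined analysis depend on comparable effects. Always report the sex-specific estimates, the pooled estimate adjusted for the stratification factors, and the arm-by-sex interaction, each with a confidence interval. Before outcome data are seen, name one deciding rule. The choice is the sponsor's.

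**(a) Keep the sex-specific design.** Restate Hypothesis 1.1.a as one hypothesis per sex. Replace the 0.05 sentence with wording such as: *The two sex-specific week-10 comparisons are tested with Holm's method at overall two-sided 0.05: the smaller p-value against 0.025 and, only if it passes, the larger against 0.05. Efficacy is claimed only for the sex or sexes that pass.* Label the pooled result supportive. Restate the per-sex detectable effect as about 0.46 if the effect is shared and 0.49 if the other sex has none. The cost is per-sex power at 0.45 of 78% or 72% respectively, in place of 81%. No extra participants are needed if that is accepted. Holding 80% power at 0.45 would take 84 evaluable per arm per sex (84 × 4 = 336) or 95 (95 × 4 = 380), in place of 320.

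**(b) Make the pooled week-10 test the single primary**, whatever the sex-specific estimates show, and relabel the sex-specific analyses and their power statement as supportive. This holds 5% and detects 0.31. It reverses the declared by-sex design. If only one sex responds at 0.45, power is 52%, against 72% for that sex under Holm.

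Under either option, state beside the sentence on adjusted and unadjusted p-values which one decides the primary endpoint.
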